## **15. STATISTICAL CONSIDERATIONS**

### **15.1 Endpoints**

#### **15.1.1 Primary Objectives**

Phase I: The Phase I primary endpoint is safety and tolerability as described in Section 3.1.1. Tolerability and safety of will be determined after all patients have completed six doses or have discontinued dosing prior to completing six doses. Safety analyses will be performed in all treated subjects. Descriptive statistics of safety will be presented using National Cancer Institute (NCI) Common Terminology Criteria for Adverse Events (CTCAE) version 4.0.

Phase II: The Phase II primary endpoint is to determine the relapse free survival rate at a median followup of 2 years in early stage NSCLC treated with definitive SBRT combined with 6 cycles of concurrent and adjuvant Avelumab.

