#### **15.2 Sample Size/Accrual Rate**

Phase I: The purpose of the Phase I part of this study is to evaluate the tolerability and safety profile SBRT combined with concurrent and adjuvant Avelumab at 10mg/kg. For this purpose, 12 subjects will be enrolled. Although the sample sizes are not based on statistical power considerations, data from these subjects will provide toxicity and dosing information on administration Avelumab in combination with SBRT in patients with early Stage NSCLC. The accrual rate is estimated at 3 patients per month.

Phase II: The primary endpoint will be relapse free survival (RFS) rate at median followup of 2 years. The accrual rate is estimated at 3 patients per month, and the patients will be

followed for up to 3 years. A total of 56 patients will be entered in the study accounting for a 10% dropout rate. This study would have 80% power to detect a 10% absolute improvement in RFS at 2 years from 80% to 90% using a one-sided t-test at significance level 0.10. RFS estimate at 2 years was based upon analysis of relevant literature[55-57].

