### 15.3 Safety Run-In Phase

There is no significant published experience with SBRT used concurrently with Avelumab in this study population. Therefore, to ensure that the combination is safe, the first six patients will be treated and observed for toxicity for 30 days after radiation before continuing with further treatment. 6 patients will be enrolled at the proposed dose of Avelumab and SBRT. If  $\leq 3$  patients among the safety cohort have a defined toxicity event within 30 days of therapy, we proceed with additional accrual with this regimen to complete a total of 12 patients. If  $\geq 4$  patients among the safety cohort have defined toxicity events we will suspend the study and have the study reviewed by IRB and DSMB committees for further recommendations.

*Toxicity Event:*  $\geq$  grade 3 adverse event (CTCAE v 4.0) with an attribution of possible, probable, or definite.

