### 15.4 Analysis of Primary Objectives

Phase I: If no more than one-third of the subjects permanently discontinue study medication prior to completing six doses due to treatment related adverse events then this combination will be deemed as tolerable and return to the IRB, DMC, and Sponsor for further evaluation and approval prior to proceeding to the Phase II cohort.

If  $\geq 4$  patients in the Phase I cohort permanently discontinue study medication prior to completing six doses due to treatment related adverse events then we will suspend the study and return the study to the IRB and DSMB committees for further evaluation and recommendations.

Phase II: The primary efficacy analysis will be the relapse free survival (RFS) rate in patients with early Stage NSCLC receiving SBRT combined with concurrent and adjuvant Avelumab compared to SBRT alone historical controls. The analysis population includes all registered subjects who have received SBRT and at least 2 cycles of Avelumab.

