### 15.5 Analysis of Secondary Objectives

- To determine whether SBRT combined with concurrent and adjuvant Avelumab results in improved loco-regional control, relapse free survival, and overall survival we will evaluate the recist criterion scans and survival rates at 6 months, 12 months and 24 months.
- To analyze whether SBRT combined with concurrent and adjuvant Avelumab impacts anti-tumor immune responses we will perform immunologic assays quantifying lymphocyte specificity and activation, including Immune cell Sequencing, ProtoArrays, Immunoassays, cell free DNA analyses, and multiparametric flow cytometry.
- Hazard rate estimates and 95% confidence intervals as well as Kaplan-Meier (KM) estimates will be used to summarize survival (OS), progression free survival (RFS), time to locoregional progression (TTLP) and time to distant progression (TTDP),

duration of response functions over time, and stable disease (SD). The median OS, PFS, TTLP, TTDP, and SD will be reported.

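### The primary RFS endpoint is worded by median follow-up, powered as 2-year RFS with a t-test that cannot handle censoring, and not tied to the 24-month Kaplan-Meier estimate; on the data cut that wording suggests, power is about 68-70%, not 80%

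*Combined protocol and SAP*

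**What the plan says.** Section 15.1.1 gives the Phase II primary endpoint as "to determine the relapse free survival rate at a median followup of 2 years in early stage NSCLC". Section 15.2 repeats it: "The primary endpoint will be relapse free survival (RFS) rate at median followup of 2 years". The power statement in 15.2 concerns "improvement in RFS at 2 years from 80% to 90% using a one-sided t-test at significance level 0.10", with 80% power, and the size is set by "A total of 56 patients will be entered in the study accounting for a 10% dropout rate". Accrual is put at 3 patients a month.

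Section 15.4 reads "The primary efficacy analysis will be the relapse free survival (RFS) rate in patients with early Stage NSCLC", compared with historical controls treated with SBRT alone. It names no estimator, test, time point or data cut.

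Three other places bear on the point:
- 11.5.3 defines RFS as a time to event from the start of treatment, with event-free patients censored at the last visit.
- 6.4 says that RECIST measurements at 6 months, 1 year and 2 years are to determine RFS.
- 15.5, on secondary objectives, covers RFS at 6, 12 and 24 months and says that hazard rates "as well as Kaplan-Meier (KM) estimates will be used to summarize survival (OS), progression free survival (RFS") and other time-to-event outcomes.

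**The concern.** A median follow-up of 2 years describes how mature the data are. RFS at 2 years is a probability at a fixed time. The plan uses the first to state the endpoint and the second to size the trial, and the analysis section does not say how they fit together.

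A t-test treats each patient's 2-year status as known. If the analysis is run at a median follow-up of 2 years, half the patients have been followed for less than that, and most of those will be event-free and censored. The plan has no rule for them in the RFS analysis. Section 15.7 counts unassessable patients as failures, but only for response rate.

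This is a single-arm, open-label trial and this is its one test against a fixed benchmark. Whether such patients are dropped, counted as successes or handled by Kaplan-Meier can decide which side of 80% the result falls on. The quoted power also depends on the choice.

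**Working it through.** **1. The plan's own figure.** Inputs from 15.2: null 0.80, alternative 0.90, one-sided 0.10, power 0.80, 56 entered, 10% dropout.
- Normal approximation: n = (1.2816·√0.16 + 0.8416·√0.09)² / 0.10² = (0.5126 + 0.2525)² / 0.01 ≈ 58.5, so 59 evaluable, or 66 entered after dividing by 0.90.
- One-sample t-test with SD √[(0.16 + 0.09)/2] = 0.354: 58 evaluable, 65 entered. At n = 56 with no dropout its power is 79.4%.
- Evaluable number under the plan: 56 × 0.90 = 50.4, about 50. The same t-test then has power 76%.

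So 56 gives roughly 80% only if nobody drops out. This shortfall exists before any question about the cut.

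**2. Patients without a 2-year status at the median cut.** Assumptions: 56 patients entering evenly at 3 a month, constant hazard, no dropout, and median potential follow-up (time from entry to cut) of 24 months.
- Entry of patient i is i/3 months, i = 0 to 55. Median entry is 9.17 months, so the cut falls at 33.17 months.
- Potential follow-up runs from 14.8 to 33.2 months. The 28 patients below 24 months average 19.3.
- Share without status = (28/56) × mean of S^(f/24) over those 28, where f is follow-up and S the true 2-year RFS.
- S = 0.80: 0.5 × 0.836 = 0.418. S = 0.90: 0.5 × 0.919 = 0.459.

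| Meaning of median follow-up | True RFS 80% | True RFS 90% |
|---|---|---|
| Potential follow-up, no dropout | 42% | 46% |
| Potential follow-up, 10% dropout by 2 years | 47% | 51% |
| Event-free patients only, no dropout | 39% | 44% |
| Observed time, relapse or death ending follow-up | 31% | 41% |

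The holds in 15.3 ("the first six patients will be treated and observed for toxicity for 30 days after radiation before continuing with further treatment") and 15.4 ("further evaluation and approval prior to proceeding to the Phase II cohort") do not change the 42-46%: with assumed pauses of 3 to 12 months between phases the share is the same.

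**3. Size and power of Kaplan-Meier at 24 months.** Simulation with exponential RFS; reject 80% if the one-sided 90% log-log lower bound exceeds it.

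| Data cut | Patients | Size | Power |
|---|---|---|---|
| Median potential follow-up 24 months | 50, no dropout | 0.094-0.100 | 68% |
| Same | 56, 10% dropouts censored | 0.093 | 70% |
| All past 24 months | 56, 10% dropouts censored | 0.086 | 74% |
| All past 24 months | 50 complete (rejects at 44/50 or more) | 0.103 | 77% |

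At the median cut with n = 50 the mean estimate is 0.799-0.800 under 80% and 0.900 under 90%, so there is no bias. At n = 50, power is 66% at 2 patients a month and 70% at 4. If relapse or death ends follow-up in the median, it is 71%.

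The two bottom rows differ in size. With 50 complete patients the rule slightly exceeds 0.10. The exact binomial rule that stays within it (45/50 or more) has size 0.048 and power 62%.

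**4. Cost of the cut.** 74 − 70 = 4 points with 56 entered; 77 − 68 = 9 points with 50 complete. What then remains to 80% (6 and 3 points) is present with full follow-up and belongs to the sample size.

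**5. Timing of the 24-month scan.** By 6.3.2 and 6.5, SBRT starts 3-10 days after the first avelumab dose and takes 4-5 fractions every other day. It therefore ends about 3 + 6 = 9 to 10 + 8 = 18 days after RFS time zero. The calendar counts visits from SBRT completion, ±10 days at 24 months. The scan thus falls from 1 day before to 28 days after 24.0 months on the RFS clock. A landmark at exactly 24.0 months would miss most relapses first documented on it.

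**6. Delay from waiting.** The last patient enters at 55/3 = 18.3 months and reaches 24 months at 42.3. 42.3 − 33.2 ≈ 9.2 months, or about 10.1 with the 28-day allowance.

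**The case against.** The strongest reply is that the pieces are all present. Section 15.2 sizes the trial on RFS at 2 years, 6.4 intends the 2-year measurement to determine RFS, and 15.5 gives both a 24-month evaluation and Kaplan-Meier for RFS. Median follow-up of 2 years can be read as the maturity required and 2-year RFS as the quantity estimated. The t-test appears only in the sample-size sentence, and 15.4 does not adopt it. Much of this stands: a reader who infers that the plan lacks a time point or a suitable estimator goes too far. What is missing is the link. Kaplan-Meier sits under secondary objectives, no text ties it to the 80% benchmark, and the only test named cannot use censored data.

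Three other stronger readings fail:
- That the primary result will be biased or its type I error inflated. With Kaplan-Meier at the median cut neither occurs; the harm depends on a t-test or simple proportion being used.
- That the median cut explains the whole gap to 80%. It explains about 4-9 points.
- That the follow-up schedules or 6.6 contradict the endpoint. RFS has one origin, the start of treatment; 6.4, 11.1 and the calendar all include 6, 12 and 24 months; and the 3 years in 6.6, under duration of follow-up, agree with the per-patient follow-up in 15.2. Only the scan-window detail matters here.

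It is also fair that the 42-46% rests on a definition the plan does not give, hence the 31-51% range.

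**Conclusion.** The point holds as a defect of specification with a moderate cost in power. The endpoint wording, the power statement and the analysis section do not define one primary analysis, and the named test does not suit censored RFS.

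At a cut with median potential follow-up of 24 months, about 42-46% of patients have no 2-year status (about 31-51% across definitions and with dropout). Kaplan-Meier is valid there, with power of about 68-70%. With everyone past 24 months it is about 74% (56 entered, 10% dropouts censored) to 77% (50 complete, actual size 0.103). Neither cut delivers the stated 80%.

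These figures assume a constant hazard, even accrual at 3 a month, exact event times and, where dropouts are modelled for power, uniform loss over 24 months. The wording defect depends on none of them.

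**What to change.** Use one definition in 15.1, 15.2 and 15.4:
- **Endpoint and test.** Kaplan-Meier RFS at the 24-month assessment, measured from the start of treatment. Reject 80% if the one-sided 90% log-log lower bound exceeds it. This replaces the t-test.
- **Window rule.** Set the landmark at the end of the 24-month visit window, or assign events found on that scan to 24 months, so that relapses first documented there count.
- **Data cut.** Either (a) all patients past the 24-month window, with power restated as about 74% for 56 entered with 10% dropout; or (b) the median-follow-up cut, with median follow-up defined and power restated as about 68-70%.

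The change is wording if the lower power is accepted. Option (a) delays the read-out by about 9-10 months at 3 patients a month (14-15 at 2, 7-8 at 4). Phase I pauses move both dates equally, and each patient's 24-month visit is already within the planned 36 months. Option (b) costs no time.

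Regaining 80% is a separate sample-size decision. For scale, the smallest exact binomial design within 0.10 needs 63 evaluable patients (55 or more relapse-free; size 0.094, power 82.5%), which is 63/0.90 = 70 entered.

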#### **15.2 Sample Size/Accrual Rate**

Phase I: The purpose of the Phase I part of this study is to evaluate the tolerability and safety profile SBRT combined with concurrent and adjuvant Avelumab at 10mg/kg. For this purpose, 12 subjects will be enrolled. Although the sample sizes are not based on statistical power considerations, data from these subjects will provide toxicity and dosing information on administration Avelumab in combination with SBRT in patients with early Stage NSCLC. The accrual rate is estimated at 3 patients per month.

Phase II: The primary endpoint will be relapse free survival (RFS) rate at median followup of 2 years. The accrual rate is estimated at 3 patients per month, and the patients will be

followed for up to 3 years. A total of 56 patients will be entered in the study accounting for a 10% dropout rate. This study would have 80% power to detect a 10% absolute improvement in RFS at 2 years from 80% to 90% using a one-sided t-test at significance level 0.10. RFS estimate at 2 years was based upon analysis of relevant literature[55-57].

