## 1. PROTOCOL SYNOPSIS

TITLE	A Phase I/II Study of Stereotactic Body Radiation Therapy (SBRT) combined with concurrent and adjuvant Avelumab for Definitive Management of Early Stage Non-Small Cell Lung Cancer (NSCLC).
STUDY PHASE	Phase I/II
INDICATION	Patients with Stage I node negative NSCLC
PRIMARY OBJECTIVES	
ξ Phase I: To assess the safety and tolerability of definitive SBRT combined with concurrent and adjuvant Avelumab in patients with early stage NSCLC.
 
ξ Phase II: To determine whether definitive SBRT combined with concurrent and adjuvant Avelumab improves relapse free survival as compared to SBRT alone historical controls.

SECONDARY OBJECTIVES	
ξ To determine whether definitive SBRT combined with concurrent Avelumab improves loco-regional control as compared to SBRT alone historical controls
 
ξ To assess overall survival in patients after completion of SBRT in combination with Avelumab
 
ξ To monitor immune correlates and anti-tumor immune responses in patients undergoing SBRT combined with concurrent Avelumab.

HYPOTHESES	
Phase I: Definitive SBRT with concurrent and adjuvant Avelumab for early stage NSCLC can be delivered safely with limited toxicity.
 
Phase II: Definitive SBRT with concurrent and adjuvant Avelumab for early stage NSCLC will result in a 10% absolute improvement in relapse free survival compared to SBRT alone historical controls.

STUDY DESIGN	This is a single arm open label Phase I/II study that will consist of two parts. The Phase I will assess the safety and tolerability of SBRT combined with Avelumab. In Phase II we will determine whether SBRT combined with Avelumab improves relapse free survival. Patients with Stage I NSCLC who are not undergoing surgical resection will be candidates for enrollment. Patients will receive definitive stereotactic body radiation (SBRT) in 4-5 fractions combined with concurrent and adjuvant Avelumab at 10mg/kg for a total of 6 cycles. Patients will be evaluated for safety as measured by the occurrence of adverse events, serious adverse events, and laboratory abnormalities. In addition, at the UCSD site, three blood draws will be obtained to analyze anti-tumor immune responses and immune correlates.
SAMPLE SIZE BY TREATMENT GROUP	Phase I: 12 Patients Phase II: 44 Patients

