### **11.5.3 Clinical Response Parameters**

**Time to Local Progression (TTLP)** is defined as the elapsed time from the start of treatment to the date of documented local progression or death, whichever happens earliest.

**Relapse-Free Survival (RFS)** is defined as the time from starting treatment to the time of first documented tumor progression or death due to any cause, whichever occurs first. Death is considered as an event here. For subjects whose disease does not progress or who do not die, PFS will be censored at the time of the last visit.

**Time to Progression (TTP)** is defined as the time from starting treatment to the time of first documented tumor progression. Subjects who do not progress will be censored at the time of the last contact. In addition, death from any cause will also be censored.

**Overall Survival (OS)** is defined as the time from starting treatment until death due to any cause. For subjects who do not die, time to death will be censored at the time of last contact.

**Locoregional Control (LRC)** is defined as the time from starting treatment until local and/or regional relapse is documented

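### The 56 patients match the evaluable number before dropout, and the only test named for the primary endpoint neither delivers the stated alpha and power nor handles censoring

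*Combined protocol and SAP*

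**What the plan says.** - **Size and power (Section 15.2).** "A total of 56 patients will be entered in the study accounting for a 10% dropout rate". The stated power is 80% for an improvement in 2-year RFS from 80% to 90%, "using a one-sided t-test at significance level 0.10". Accrual is 3 patients per month and follow-up lasts up to 3 years. No SD, formula or evaluable number is given.
- **Split by phase (Synopsis).** 12 patients in Phase I and "Phase II: 44 Patients", which together make 56. The design is single arm.
- **Timing (Section 15.1.1).** The Phase II endpoint is the "relapse free survival rate at a median followup of 2 years".
- **Endpoint (Section 11.5.3, under RFS).** RFS is a time to event: "For subjects whose disease does not progress or who do not die, PFS will be censored at the time of the last visit".
- **Primary analysis (Section 15.4).** The RFS rate is compared with historical controls and no test is named. "The analysis population includes all registered subjects who have received SBRT and at least 2 cycles of Avelumab".
- **Other RFS text.** Section 15.5, under secondary objectives, uses Kaplan-Meier and hazard estimates with 95% confidence intervals to summarise RFS. Sections 6.4 and 15.5 also plan assessments at 24 months. None of these sets a test against 80%.

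**The concern.** If 56 is the number entered after allowing for 10% dropout, the calculation should have started from about 50 evaluable patients. The usual formulas for these rates start from about 56. That suggests the allowance is described but was not applied.

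The named test raises a separate problem, whatever variance was assumed. A t-test on a 2-year rate needs a yes/no status at 2 years for every patient. At a median follow-up of 2 years, about half the patients have not been observed that long, and the RFS definition censors them. If the plan does not say how they enter the comparison, the primary result can depend on a choice made after the data are seen. The single-arm conclusion about RFS rests on this one comparison.

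**Working it through.** **Inputs.** From Section 15.2: null 0.80, alternative 0.90, one-sided alpha 0.10 (z = 1.2816), power 80% (z = 0.8416), 56 entered, 10% dropout, 3 patients per month. From the Synopsis: single arm, so one sample against a fixed rate. The SDs are √(0.8×0.2) = 0.40 under the null and √(0.9×0.1) = 0.30 under the alternative.

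**Step 1: where 56 comes from.** Evaluable number needed:

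- Null and alternative variance: [(1.2816×0.40 + 0.8416×0.30)/0.10]² = 58.5.
- Averaged variance, (0.16+0.09)/2 = 0.125: (2.1232)² × 0.125/0.01 = 56.3.
- Arcsine, h = 2·arcsin√0.9 − 2·arcsin√0.8 = 0.2838: (2.1232/0.2838)² = 55.97.
- Average SD 0.35: (2.1232×0.35/0.10)² = 55.2.
- Alternative SD 0.30 throughout: (2.1232×0.30/0.10)² = 40.6.

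The arcsine formula gives 56 before any dropout. Adding the allowance gives 56/0.9 = 62.2, so 63 entered. From 59 evaluable it gives 65.6, so 66. With SD 0.30 it gives 41/0.9 = 45.6, so 46. None of these gives 56 after inflation.

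**Step 2: power after dropout.** 56×0.9 = 50.4. At n = 50:

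- Normal approximation: Φ[(0.10×√50 − 1.2816×0.40)/0.30] = Φ(0.648) = 0.742.
- Arcsine: Φ(0.2838×√50 − 1.2816) = Φ(0.725) = 0.766.

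**Step 3: the named t-test on 0/1 data.** The test uses the sample SD, which falls below the null value of 0.40 when the observed rate is high. Take n = 50, with critical value 1.299 on 49 degrees of freedom. For 43 relapse-free, t = 0.06/0.0496 = 1.21, which does not reject. For 44, t = 0.08/0.0464 = 1.72, which rejects. The size is therefore P(X ≥ 44 | 0.80) = 0.103 and the power is P(X ≥ 44 | 0.90) = 0.770. The size moves between 0.092 and 0.160 as the evaluable number runs from 46 to 56. Averaged over Binomial(56, 0.9), size is 0.123 and power 0.800. For 44 entered, about what SD 0.30 would suggest, the averages are 0.142 and 0.758.

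**Step 4: how many are short of 2 years.** With one entry every 1/3 month, the median entry is at 27.5/3 = 9.2 months and the last at 55/3 = 18.3 months. When median time since entry reaches 24 months, 28 of 56 patients have under 24 months. Waiting until the last patient reaches 24 months takes 18.3 − 9.2, or about 9 months more. The run-in rule ("the first six patients will be treated and observed for toxicity for 30 days after radiation before continuing with further treatment") and the review before Phase II do not change this gap, because the second half of the patients enter after them.

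**Step 5: tests that handle censoring.** Simulation with 56 entered. Assumed: exponential dropout reaching 10% at 24 months, and Weibull event times with shape 0.7, 1.0 or 1.5. The log-rank rows also assume that the shape of the null curve is known.

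| Test | Data cut | Size | Power |
|---|---|---|---|
| Kaplan-Meier at 2 years, complementary log-log | all to 24 months | 0.082-0.086 | 0.740-0.749 |
| Same | median 24 months since entry | 0.092-0.096 | 0.678-0.718 |
| One-sample log-rank | all to 24 months | 0.090-0.097 | about 0.81-0.87 |
| Same | median 24 months since entry | 0.082-0.088 | 0.744-0.757 |

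With no dropout, full follow-up and shape 1.0, the Kaplan-Meier test on 56 has size 0.103 and power 0.802. That is the pattern expected if dropout was left out.

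**The case against.** **The missing allowance is inferred.** The plan does not state its variance or formula. SD 0.30 needs only about 41 evaluable. A one-sample log-rank calculation needs about 44 to 59, depending on follow-up. An intermediate case of 50 would give 50/0.9 = 55.6, so 56 entered. This stands: a reader might infer a proven sample-size error, and the documents do not support that. It does not rescue the text as written, because Section 15.2 names a t-test and not a log-rank test.

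**A valid test can reach 80% with 56 entered.** The one-sample log-rank test does so if every patient is followed to 2 years, because it uses information after 24 months. This also stands. A reader might infer that any test holding alpha at 0.10 falls short, or that more patients are needed. Neither follows. The shortfall applies to the named t-test and to tests of the 2-year rate. The log-rank result in turn needs a historical curve, and the plan gives only a 2-year value.

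**The lower figures depend on reading and assumptions.** If median follow-up means observed follow-up, the cut falls later and Kaplan-Meier power is about 71-74% instead of 68-72%. The bottom of each range comes from shape 1.5. The 10% might also mean patients outside the Section 15.4 population, and Section 6.7 follows withdrawn patients for survival, so some would still contribute deaths. These points are fair, and they are reasons for the plan to define both terms.

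**A 24-month landmark is planned.** Sections 6.4 and 15.5 do assess RFS at 24 months. That shows the intended time point but supplies neither a test nor a rule for patients censored earlier.

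**Conclusion.** The point holds with two limits. First, 56 agrees with the evaluable number from standard one-sample formulas (about 55 to 59), so the 10% allowance does not appear to have been added. Without the sponsor's formula this remains an inference. Second, for the test that the plan names, the stated alpha and power do not both hold. With about 50 evaluable, a test of the 2-year proportion has about 74-77% power. The t-test on 0/1 data averages 80% power only with a type I error of about 12%.

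The gap over censoring does not depend on the variance. No primary test in the plan can use RFS times censored before 2 years. The documents do not show that 56 is too few for every valid test; that depends on the test and data cut chosen. The power ranges in Step 5 rest on assumed dropout timing and event-time shapes.

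**What to change.** 1. In Sections 15.2 and 15.4, replace the t-test with one primary test that handles censoring. One choice is a one-sided 0.10 test of the Kaplan-Meier 2-year RFS against 80% on the complementary log-log scale, reported with its one-sided 90% lower confidence limit. The untransformed Greenwood version has a size of about 13-14%. A one-sample log-rank test is an alternative if the whole historical curve, not only its 2-year value, is specified in advance.
2. State the data cut, and define median follow-up as time since entry or as observed follow-up. Change Section 15.1.1 as well if the full 2-year cut is chosen.
3. Restate the power of the chosen test with 56 entered and 10% dropout, and give the formula, variance and evaluable number. For Kaplan-Meier, expect about 74-75% at the full cut or 68-72% at a median time since entry of 2 years. For log-rank, expect about 81-87% or 74-76%.
4. Confirm in Section 15.4 that the 56 include the 12 Phase I patients, as Section 15.2 implies. With 44 evaluable alone, a proportion test has about 69-73% power.

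**Cost.** Wording only, with no extra patients. The downside is a possibly lower stated power, or an analysis about 9 months later at the full cut. That cut needs 24 of the up to 36 months of follow-up planned per patient. Holding the Kaplan-Meier test at 80% with full follow-up would instead take about 64-65 entered, or 8-9 more.
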